7.2 Study Procedures

Subjects will be invited for initial consultation performed by the study PI. This will be completed at the GCRC. If subjects are not currently in the Penn State system, they will be registered prior to this consultation through the Penn State Gastroenterology/Hepatology clinic staff ([name] or [name]). For all individuals who provide signed, informed consent, the following baseline measures will be completed:

- Comprehensive history and physical examination
- Anthropometric assessment [height, weight, BMI calculation]
- Physical activity questionnaire (IPAQ)
- Urine Pregnancy Test
- Nutrition counseling will be provided by a Registered Dietitian (RD) to promote a hypocaloric, low-fat dietary intake pattern. In the case that Dietitians are unavailable in person, counseling will be completed by phone or video chat using the Penn State Health-branded Zoom. Food Frequency Questionnaire (FFQ) will be used to assess their current dietary practices. Individual caloric needs will be calculated at baseline using the Mifflin St. Jeor equation, providing resting energy expenditure (REE), multiplied by the appropriate activity factor (AF) to yield total energy expenditure (TEE). Adjusted body weight (ABW) will be used when the participant's BMI is equal to or greater than 30. Five-hundred to 750 calories will be subtracted to promote an approximate weight loss of 1 pound per week for participants whose BMI classifies as overweight or obese. Macronutrient distribution will be recommended at 50-60% carbohydrate, 15-20% protein, and 20-30% fat with <10% total calories attributable to saturated fat. A sodium intake of <2,000 mg daily will be encouraged.

ABW & IBW Calculations:

- Use ABW to calculate REE when BMI ≥ 30
 - ABW calculation:
 - Males: $IBW + 0.38 \times (BW - IBW)$
 - Females: $IBW + 0.32 \times (BW - IBW)$
 - IBW calculation:
 - Males = $106 + 6 \times (Ht.(in)-60)$
 - Females = $100 + 5 \times (Ht.(in)-60)$

REE via Mifflin St. Jeor Equation:

- Male: $10(wt. (kg)) + 6.25(ht. (cm)) - 5(age (yr)) + 5 = REE \times AF = TEE$
- Female: $10(wt. (kg)) + 6.25(ht. (cm)) - 5(age (yr)) - 161 = REE \times AF = TEE$

| Activity Factors: | |
|--|--|
| Lifestyle and Physical Activity Level (PAL) | |

| | |
|--|---------------------|
| Seated work with no option of moving around and little or no strenuous leisure activity | 1.4-1.5 |

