Following their assessment and randomization, subjects will undergo baseline VO2 max testing at the Penn State Physical Medicine and Rehabilitation (PMR) Research Laboratories under the supervision of ACSM certified trained fitness professionals and study physicians. Anthropometric measurements will be completed at this assessment as well with dual-energy x-ray absorptiometry (DXA) body composition measurement, waist circumference, hip circumference and skin fold measurement. Following this, subjects will be given a Fitbit Charge2 with heart rate (HR) monitor along with an instruction form on how to use dietary log. Formal instruction on how to use the Fitbit Charge2 will be provided by trained study staff. This will include technical support with the Fitbit app that is supported on smartphones, the Fitbit website and Fitabase, a secure comprehensive data management platform for research studies, clinical trials and healthcare innovation projects utilized by >400 clinical trials since its inception. Participants will be instructed to record their food and beverage intake in a daily food diary through the Fitbit app and be provided information on how closely their daily food intake met the goals for macronutrients and energy.

Moderate intensity aerobic exercise: Subjects in the aerobic exercise group will be supervised to exercise 30 minutes, five times per week at a moderate intensity (HR target corresponding to 45-55% of their VO2max). Formal exercise instruction and supervision will be provided by ACSM certified fitness professionals at the Penn State University Fitness Center. Subjects will initiate their exercise program by walking on a treadmill for 15 minutes at their target HR goal and progressively increase the duration and frequency until the goal of 30 minutes of moderate intensity exercise five times a week is reached by the end of the four-week lead-in period. Subjects will then exercise five times a week under direct supervision in one of three locations; the Penn State University Fitness Center, the Cancer Center

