Exercise Medicine Unit or the Hershey Center for Applied Research. Aerobic exercise can be completed on either the treadmill, exercise bike, rowing machine or the elliptical machine. Subjects will be given the opportunity to complete these supervised sessions virtually or in-person as described above. If the subject chooses to complete the strength training sessions virtually, the study EP will schedule and complete exercise sessions using Penn State HIPAA complaint Zoom. Additional home exercise beyond the recommended sessions will be assessed by downloading data from the Fitbit Charge2. Review of downloaded information will take place once a week. Any subject who performs <3 sessions in any given week during the 16-week study period will be required to extend their training by two additional weeks to offset loss of physical conditioning. They can be extended no longer than 4 weeks. If subject misses more than 2 weeks of exercise sessions, they will be discontinued from the study.

Weekly review of dietary logs obtained via self-report through the FitBit application and secure web-based platform with directed feedback by trained study personnel (nutritionist) will also be provided either in-person, telephone interview or video chat. Additionally, participants will be given dietary education forms. In the event that the subject does not self-report their dietary intake through the FitBit platform, the 24-hour dietary recall data collection form will be utilized.

Study investigators will perform an interim history and physical examination on a monthly basis during the exercise protocol. If subject is required to extend protocol, interim history and physical examinations will continued to be performed on a monthly basis. The subject may complete these either in person or virtually.

The purpose of the post-exercise program liver biopsy is to observe changes in stage of fibrosis and NASH Activity Score. Liver biopsy is the gold standard to stage chronic liver disease from NASH and the benefit of disease staging and prognostication outweighs the small risk to the subject. Non-invasive methods of diseases staging (serologic scoring systems NFS, FIB-4) and ultrasound with elastography have inferior performance characteristics with much lower sensitivity and specificity and are hindered by significant inaccuracy with misclassification bias observed in upwards of 25%.(1, 93) Sub-

[REDACTED]

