Penn State University Fitness Center: Housed with the Penn State University Conference Center, the University Fitness Center has a plethora of resources including free weights and cardiovascular equipment necessary for this protocol. In addition, group fitness classes, gymnasium, locker room and shower facilities are available during convenient all-day hours, 7 days a week. In addition to the dedicated NASHFit exercise physiologist, there are an additional seven exercise physiologists on staff. There are private rooms available for study visits allowing for completion of assessment immediately before or after an exercise session by trained study personnel.

Follow-up. Subjects will be seen by a study investigator immediately after the completion of the 16-week exercise intervention. This will be completed at the Penn State Hershey GCRC and the PM&R research laboratory. A focused history and physical exam, anthropometric assessment including DXA scan, IPAQ, dietary log, cardiopulmonary fitness testing, laboratories, stool sample, MRI-PDFF, PROMIS and end of study survey will be completed. A sub-study of ten subjects will be required to complete a liver biopsy following sub-randomization at the completion of the exercise intervention. Samples collected for research purposes will be stored per standard SOP requirements of the Pathology Department. Subjects will be compensated (\$25 at baseline, \$25 at completion of the exercise regimen, \$100 following liver biopsy obtained at the completion of the exercise regimen if selected). They will also be allowed to keep their FitBit Charge2 HR. Finally, participants will receive a list of local fitness facilities available in the area. Twelve weeks after the end of the program, study staff will contact participants in the exercise arm by phone to complete a follow up questionnaire.

Paired liver biopsy samples (enrollment sample and post-exercise sub randomized sample) will be sent to a biotechnology company, Reveal Biosciences, to undergo an automated computerized ImageDx analysis to evaluate the severity of NASH. Samples will be shipped directly from the Pathology (where they are stored) and they will be de-identified.

Schedule of visits and study protocol assessments

| Visit | Initial Assessment | Exercise Instruction | Exercise Program or Control | End of exercise program |
|---|--------------------|----------------------|-----------------------------|-------------------------|

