| Day/Week | Day 0 | Weeks 0-4 | Weeks 5-19 | Week 20 |
| Initial comprehensive history and physical exam | X | | | |
| Focused history and physical exam | | | X (monthly) | X |
| Anthropometric assessment | X | | X (monthly) | X |
| Physical activity questionnaire (IPAQ) | X | | X (monthly) | X |
| Dietary Log | | X (weekly) | X (weekly) | x |
| FitBit activity data download | | X (weekly) | X (weekly) | X |
| Cardiopulmonary fitness testing (VO2 max) | X | | | X |
| Electrocardiogram (ECG) | X | | | |
| Laboratories | X | | | X |
| Stool sample | X | | | X |
| Urine pregnancy testing (if applicable) | X | | | |
| Genetic testing | X | | | |

| | | | | |
|---|---|--|-------------|-----------------------|
| Liver MRI-PDFF | X | | | X |
| PROMIS Quality of Life Assessment via iPad (completed under direct supervision of trained research personnel) | X | | X (monthly) | X |
| DXA body composition testing | X | | | X |
| Liver biopsy | | | | X (if sub-randomized) |

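### Pregnancy is tested only at Day 0, yet DXA and the maximal exercise test are repeated at Week 20, 20 to 24 weeks later, without a new test

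*Combined protocol and SAP*

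**What the plan says.** Section 3.2 excludes pregnant subjects. Section 7.2 lists "Urine Pregnancy Test" once, among the baseline measures. The two procedures at issue come afterwards: "Following their assessment and randomization, subjects will undergo baseline VO2 max testing", and for body composition, "Anthropometric measurements will be completed at this assessment as well with dual-energy x-ray absorptiometry (DXA) body composition measurement".

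The schedule of visits in section 7.2 has four columns: Day 0, Weeks 0-4, Weeks 5-19 and Week 20. Three rows matter here:

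- "Urine pregnancy testing (if applicable) | X", with the mark under Day 0 and nothing in the later columns
- "DXA body composition testing | X | | | X", marked at Day 0 and Week 20
- "Cardiopulmonary fitness testing (VO2 max) | X | | | X", marked at Day 0 and Week 20

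The follow-up paragraph of section 7.2 agrees with the table. It says that "anthropometric assessment including DXA scan, IPAQ, dietary log, cardiopulmonary fitness testing, laboratories, stool sample, MRI-PDFF, PROMIS and end of study survey will be completed", with no pregnancy test in the list. The laboratory panel in section 7.2 does not contain one either. Section 7.3 gives the duration of participation as 20 weeks. For exercise-arm subjects who miss sessions and have their training extended, section 7.2 sets a limit: "They can be extended no longer than 4 weeks".

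**The concern.** The protocol obtains a pregnancy result before the first DXA scan and the first maximal exercise test, but not before the second of each. It gives no reason for treating the two occasions differently. Section 11.0 names the hazards: radiation from DXA, and a VO2 max test that takes the subject to exhaustion, with possible fainting and a risk of falling on the treadmill.

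Section 3.1 admits adults from 18 to under 70, so subjects who could become pregnant during the study may enrol. A site that follows the schedule exactly could give a second scan and a second maximal test to a subject with an early, unrecognised pregnancy, relying on a result from about five months before. What is at stake is the safety of a small number of subjects. The primary outcome, the sample size and the analysis are not involved.

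**Working it through.** No power or error-rate calculation applies. The check sets the schedule entries side by side and then computes the interval.

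**1. Tests against procedures (schedule and text of section 7.2)**

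| Item | Day 0 | Weeks 0-4 | Weeks 5-19 | Week 20 |
|---|---|---|---|---|
| Urine pregnancy test | yes | no | no | no |
| DXA | yes | no | no | yes |
| VO2 max | yes | no | no | yes |

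Each completing subject has 2 DXA scans and 2 VO2 max tests but 1 pregnancy test. At baseline a current test precedes 2 of the 2 procedures; at Week 20 it precedes 0 of 2. The table and the follow-up paragraph agree, so the empty cell is not a table broken in conversion.

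**2. Age of the result at the second exposure**

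- The plan's own figure: a 4-week lead-in plus a 16-week program gives 4 + 16 = 20 weeks. This matches the Week 20 column and section 7.3.
- As scheduled: 20 × 7 = 140 days.
- With the maximum extension, exercise arm only: (20 + 4) × 7 = 168 days.
- Controls have no training to extend and stay at 140 days.
- Alternative reading: the follow-up paragraph places the visit directly after the 16-week intervention. If the lead-in is counted inside those 16 weeks, the interval is 16 × 7 = 112 days, or (16 + 4) × 7 = 140 days with the full extension. The schedule and section 7.3 favour 20 weeks as the base.

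**3. Other places that could close the gap**

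- Section 3.3.1 (removal criteria) does not mention pregnancy.
- Section 7.2 schedules a focused history and physical examination monthly and at Week 20. Neither a pregnancy question nor a test is specified. The monthly visits may be virtual in both arms.
- Section 11.0 names pregnancy testing as a source of incidental findings, to be handled at the investigator's discretion. That covers what follows a positive result; it does not schedule a test.

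**4. Upper bound on added tests**

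- All enrolled subjects: 42 (section 8.1).
- After the 15-20% attrition in section 8.2: 42 × 0.80 = 33.6 to 42 × 0.85 = 35.7, so about 34 to 36.
- Only applicable subjects would be tested, so the real number is lower. The documents do not give the sex and age mix, so it cannot be narrowed further.

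**The case against.** The best defence is that the single test does what the protocol asks of it. Pregnancy is an entry exclusion, not a removal criterion, and nothing says that it is excluded because of DXA or VO2 max. On that view the test establishes eligibility, no stated rule is broken, and a second test is a preference. It stands that this is a design choice and not a contradiction. It does not explain why hazards named in section 11.0 should be met with a current test on one occasion and not on the other.

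Second, the Week 20 visit is in person, with an investigator's history and examination, so the virtual option for monthly visits says little about the check available on that day. This is fair, and the virtual option carries little weight here. But a history can miss an early pregnancy, which is exactly what a urine test is for.

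Third, the harm is not quantified: the documents give no DXA dose, no fetal risk and no count of subjects who could become pregnant. This stands and limits the point to a minor one.

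Fourth, a Week 20 test would not detect pregnancy during the months of training and caloric restriction. That is true. The proposal addresses only the second DXA and VO2 max test.

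Finally, the consent pages and the separate radiation review form were not available, and either could contain an instruction on pregnancy. The finding is therefore limited to the protocol text supplied.

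**Conclusion.** The point holds. As written, the plan repeats a radiation procedure and an exhaustive exercise test at Week 20 on a pregnancy result that is 140 days old, or up to 168 days in the exercise arm. If the lead-in is counted within the 16 weeks, the interval is 112 to 140 days; the gap remains on either reading. The absence of a repeat test is certain from the text, since the table, the follow-up list and the laboratory panel all agree. How often it would matter cannot be estimated from the documents, and the event is expected to be rare. It is an inexpensive safety improvement worth considering, with no bearing on the validity of the trial's results.

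**What to change.** In the schedule of visits, add a mark for urine pregnancy testing (applicable subjects) in the Week 20 column. In the follow-up paragraph of section 7.2, add the test and state that the result is to be available before DXA and VO2 max, as at baseline. Management of a positive result can stay with the investigator and the IRB, in line with the incidental-findings provision in section 11.0.

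The cost is one table cell, a few words of text and one urine test per applicable subject at a visit that already takes place in person. The test is already in use in the trial, and no extra visit, staff or analysis is needed. The possible downside is a rare missing end-of-study DXA or VO2 max value. VO2 max enters one of the secondary outcomes in section 1.3; the primary PAI-1 outcome is not affected.

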7.3 Duration of Participation
20 weeks- please see above table.

8.0 Subject Numbers and Statistical Plan

8.1 Number of Subjects
We expect to enroll 42 subjects.

8.2 Sample size determination
Subjects will be randomized into two treatment groups. This is an efficient study design with increased power and is appropriate for the proposed exercise intervention. The primary outcome will be change in PAI-1 following a 16-week exercise course. Secondary outcomes are described above. Baseline levels of PAI-1 are between 35-45 ng/mL.(72, 74-76) Estimates for change in PAI-1 following exercise regimens of between 3-8 months duration range between 23-37% with >30% reduction only reported in regimens >6 months long.(72, 74-76) De Gues *et al.*(75) found an initial 24.5% reduction as measured at four months in PAI-1 levels in thirty healthy adults aerobically exercising 2.5 hours per week. We expect the exercise intervention to result in a 23% reduction (9 ng/dL) in PAI-1. We expect no change in PAI-1 levels in the control arm. We conservatively determined power calculations utilizing the standard deviations in the literature (2.0 for no exercise group and 14.0 for the aerobic exercise group). We expect a 15-20% attrition rate;(94) to account for this we will enroll an additional six subjects.

Based on these assumptions and a 2:1 enrollment ratio with two subjects in the aerobic exercise arm to every one subject in the standard of care arm, a total study enrollment size of 28 subjects in the aerobic exercise arm and 14 in the standard of care arm will achieve 80.74% power to detect a difference in mean PAI-1 at sixteen weeks of at least 9 ng/mL, using a two-sided, two-sample unequal variance t-test with a significance level (alpha) of 0.05. A total study enrollment of **42 subjects** is planned.

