3.3 Early Withdrawal of Subjects

3.3.1 Criteria for removal from study

- Development of severe adverse event
- Subject consents to withdrawal
- Development of decompensated cirrhosis
- Failure to complete two successive weeks of exercise protocol.
 - Any subject who performs < 3 sessions in any given week during the 16-week study period will be required to extend their training by two additional weeks to

offset loss of physical conditioning. The power calculation accounts for expected study dropout (15-20% in exercise protocols).

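### The stated 80.74% power belongs to 22 + 11 subjects, not to the 28 + 14 it is attached to, and the six extra subjects for attrition do not connect the two

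*Combined protocol and SAP*

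**What the plan says.** Section 8.2 sets out the whole calculation. The expected effect is given by "We expect the exercise intervention to result in a 23% reduction (9 ng/dL) in PAI-1" and "We expect no change in PAI-1 levels in the control arm". The SDs are "2.0 for no exercise group and 14.0 for the aerobic exercise group". The test is described as "using a two-sided, two-sample unequal variance t-test with a significance level (alpha) of 0.05", and the aim is "to detect a difference in mean PAI-1 at sixteen weeks of at least 9 ng/mL". Allocation is 2:1.

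On attrition, the section expects 15-20% and continues: "to account for this we will enroll an additional six subjects". It then concludes that "28 subjects in the aerobic exercise arm and 14 in the standard of care arm will achieve 80.74% power", and plans a total of 42. Section 8.1 also gives 42.

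Section 3.3.1 adds: "The power calculation accounts for expected study dropout (15-20% in exercise protocols". Neither section says how many subjects must have a follow-up PAI-1 value for the stated power to hold.

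**The concern.** Section 8.2 attaches a power to the enrolled arm sizes and, in the sentence before, says that extra subjects were added for attrition. If 42 already includes that allowance, 80.74% should belong to a smaller number, and that number plus six should be 42. If 80.74% is the power of all 42, nothing has been allowed for attrition.

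The answer matters while the trial runs. Under section 3.3.1 and the exercise procedures in section 7.2, subjects are removed for missed exercise weeks. The follow-up that section 3.3.2 gives as its example for withdrawn subjects is a phone call, which yields no PAI-1 value. The number with a follow-up measurement therefore decides the power. Read literally, section 8.2 says that all 42 are needed, so almost any dropout would seem to take the trial below 80%. Read through the six extra subjects, it suggests that 36 completers are needed. These readings lead to different decisions on replacing dropouts or extending recruitment. Anyone who checks the power statement will also fail to reproduce it.

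**Working it through.** **Inputs, all from section 8.2.** Difference d = 9 ng/mL; SD 14.0 (exercise) and 2.0 (control); two-sided alpha 0.05; unequal-variance (Welch) t-test; 2:1 allocation. The section writes the effect once in ng/dL. I use ng/mL, the unit of the power sentence and of the baseline range: 23% of 35 to 45 ng/mL is 8.05 to 10.35 ng/mL.

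**Formulas.**
- SE = √(14²/n₁ + 2²/n₂)
- Satterthwaite df = (14²/n₁ + 2²/n₂)² / [(14²/n₁)²/(n₁−1) + (2²/n₂)²/(n₂−1)]
- Power = P(|T| > t with 0.975 probability below it), where T is noncentral t with that df and noncentrality d/SE

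**The plan's own case, 28 + 14.** 196/28 = 7.000 and 4/14 = 0.286, so SE = √7.286 = 2.699. Noncentrality is 9/2.699 = 3.334, df = 29.15, critical t = 2.045. Power is 89.66%, not 80.74%.

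**Which size gives 80.74%?**

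| Exercise + control | Total | SE | df | Power | Simulated (100,000 trials) |
|---|---|---|---|---|---|
| 28 + 14 | 42 | 2.699 | 29.15 | 89.66% | 89.7% |
| 26 + 13 | 39 | 2.801 | 26.99 | 87.22% | not run |
| 24 + 12 | 36 | 2.915 | 24.83 | 84.27% | 84.4% |
| 22 + 11 | 33 | 3.045 | 22.67 | **80.74%** | 80.8% |

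The match at 22 + 11 is exact to two decimals and has the stated 2:1 ratio. Neighbouring sizes miss: 22 + 12 gives 80.85%, 22 + 10 gives 80.61%, 21 + 11 gives 78.79%. In a grid search over arm sizes, no other pair came within 0.06 of a percentage point.

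**Can another method give 80.74% at 28 + 14?**
- Normal approximation: 91.5%
- df = N − 2: 90.2%
- One-sided test: 94.6%
- Common SD of 14: 48.3%
- Common SD of 10 (root mean square): 76.5%
- Pooled SD of 11.56: 64.1%
- SDs swapped between arms: 60.2%
- Alpha 0.02: 80.3%
- Difference 8.05: 82.2%

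None returns 80.74%. The only two within two points change a stated input.

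**Attrition.**
- 33 + 6 = 39 and 42 + 6 = 48; neither is 42.
- 36 + 6 = 42, but 36 has 84.27% power.
- 6/42 = 14.3%, below 15-20%.
- 42 − 33 = 9, and 9/42 = 21.4%.
- 33/(1 − 0.20) = 41.25, which rounds up to 42 at 2:1.

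**The case against.** The best defence is that 80.74% was always meant as power after dropout. The power sentence follows directly on the attrition assumption, speaks of enrolment rather than completers, and section 3.3.1 says that dropout is accounted for. The arithmetic supports this: 28 × 0.80 = 22.4 and 14 × 0.80 = 11.2, which is 22 + 11 completers and exactly 80.74%. On that reading the power, the enrolment and the upper attrition rate agree, and the one wrong item is the count of six.

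Six is also not far from the stated range if counted differently. It is 16.7% of a base of 36, and 15% of 42 is 6.3. And the error is conservative: 42 subjects have more power than claimed, and 36 completers would have 84.3%.

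Most of this stands. It probably explains where the figure came from, it shows that 42 is not too few, and it means that the 14.3% should not carry the point alone, since it depends on the denominator. It does not rescue the text. Section 8.2 does not say that 80.74% is conditional on 20% loss, and it gives no evaluable number. No reading makes an allowance of six lead from a size with 80.74% power to 42.

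**Conclusion.** The point holds. On the section's own inputs, 28 + 14 subjects have 89.7% power, 8.9 points above the stated 80.74%. The stated figure is that of 22 + 11, and the allowance that leads from there to 42 is nine, not six.

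This is an error of statement, not a shortage of subjects. Over the stated attrition range, power runs from about 84.3% (15% loss, about 36 completers) to 80.7% (20% loss, about 33). No analysis or conclusion is biased by it. What is missing is a correct evaluable target.

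Two assumptions lie behind this. The difference and the SDs are taken as the protocol gives them; whether they are realistic is a separate question. That 22 + 11 was the intended base is an inference from the exact match and the 20% link, and the sponsor should confirm it.

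**What to change.** Rewrite the end of section 8.2 along these lines, once the sponsor has confirmed the base from the original calculation:

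> With 33 evaluable subjects (22 exercise, 11 control), the two-sided unequal-variance t-test at alpha 0.05 has 80.74% power for a difference of 9 ng/mL. To allow for 20% attrition (33/0.80 = 41.25, rounded up to keep the 2:1 ratio), nine further subjects are enrolled, for a total of 42 (28 exercise, 14 control). Without attrition, power would be 89.7%.

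Delete the sentence on six additional subjects, and define evaluable as having the PAI-1 values that the primary comparison needs. Use ng/mL throughout the section. The remark on dropout in section 3.3.1 can then stand, with a cross-reference to section 8.2.

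If the sponsor finds that 36 evaluable subjects was the intended base, the text should instead give 84.3% power for 24 + 12 and say that six of 42 covers 14.3% loss.

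The cost is one paragraph of protocol wording. Enrolment, allocation and analysis do not change.

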1.2 Primary Study Endpoints

The primary outcome of interest is change in fibrinolysis as measured by PAI-1 level immediately following completion of the exercise and nutritional counseling program.

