1.3 Secondary Study Endpoints

Secondary Outcomes are as follows: (1) Change in PAI-1 after 16-week exercise regimen; (2) Change in other markers of hemostasis [von Willebrand Factor (vWF), P-selection, Protein S, Protein C, Factor VII, Factor VIII, Fibrinogen, Antithrombin,] after 16-week exercise regimen; (3) Change in PAI-1 stratified by PNPLA3 genotype after 16-week exercise regimen; (4) Correlation between loss of hepatic fat as measured by magnetic resonance imaging proton density fat fractionation (MRI-PDFF) and changes in hemostatic markers after 16-week exercise regimen; (5) Correlation between maximal oxygen consumption (VO₂ max) and hemostatic markers after 16-weeks of exercise; (6) health-related quality of life (HRQOL) change following exercise intervention

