8.3 Statistical methods
Subjects will be compared across multiple important baseline demographic, laboratory, imaging and histologic data. Results will be expressed as means with standard deviations. Chi-squared and Fisher's exact test will be used to analyze our categorical endpoints. Student's t test and Mann-Whitney Rank Sum test will be used for secondary analysis of differences in numerical lab data. Paired t-tests will be used where appropriate (e.g. comparison of pre- and post-intervention fibrosis parameters such as NFS or FIB-4 Score). A p value of <0.05 will be significant. Intention to treat analysis will be performed. Analyses will be conducted using SAS version 9.4. Multivariable regression models will be constructed.

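### The primary outcome is change in PAI-1, but 8.2 ties it to an unadjusted test of 16-week means with unlabelled SDs, and 8.3 names no primary analysis or baseline covariate

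*Combined protocol and SAP*

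**What the plan says.** **Endpoint.** Section 1.2: "The primary outcome of interest is change in fibrinolysis as measured by PAI-1 level". Section 8.2 agrees: "The primary outcome will be change in PAI-1 following a 16-week exercise course".

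**Test and SDs.** The only test tied to that outcome is in the power statement of 8.2, which is to "detect a difference in mean PAI-1 at sixteen weeks of at least 9 ng/mL, using a two-sided, two-sample unequal variance t-test". The SDs are given as "2.0 for no exercise group and 14.0 for the aerobic exercise group" and described only as coming from the literature. The 9-unit effect is a 23% fall with exercise, and for controls "We expect no change in PAI-1 levels in the control arm".

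**Analysis section.** Section 8.3 names no analysis for the primary outcome. Its two-sample tests have another role: "Student's t test and Mann-Whitney Rank Sum test will be used for secondary analysis of differences in numerical lab data". Its only reference to modelling is "Multivariable regression models will be constructed", with no outcome or covariate.

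**Design.** Section 7.2 has PAI-1 measured at baseline, with a further laboratory draw at the end of the programme. Allocation is 2:1 in blocks of six, and no stratification factor is named.

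**The concern.** Three analyses of the primary outcome remain open: week-16 level, change from baseline, or an unspecified regression. They share one expected treatment difference, because randomisation makes the arms equal at baseline on average. They differ in variance and in how far a chance baseline difference enters the estimate.

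With about 33 to 36 evaluable subjects and nothing in the allocation to balance baseline PAI-1, both matter. The size cannot be read from the protocol, because Welch power with SDs of 14 and 2 is the same number whether they describe levels or changes. The stated power therefore does not show which variable was powered.

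**Working it through.** **Inputs.** From 8.2: difference 9, SDs 14 (exercise) and 2 (control), two-sided alpha 0.05, enrolment 28 + 14, six subjects added for attrition of 15–20%. Not in the documents, so assumed: baseline SD *b* of 4 to 12 ng/mL, and the correlations below.

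**1. The stated power.** SE = √(14²/n₁ + 2²/n₂), then the noncentral t with Satterthwaite df.

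| Evaluable | SE | 9/SE | Power |
|---|---|---|---|
| 28 + 14 | √(7.000 + 0.286) = 2.699 | 3.33 | 89.66% |
| 24 + 12 (42 less six) | √(8.167 + 0.333) = 2.915 | 3.09 | 84.27% |
| 22 + 11 (42 less about 20%) | √(8.909 + 0.364) = 3.045 | 2.96 | 80.74% |

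The printed 80.74% is the 22 + 11 figure. That it is attached to 28 + 14 is a separate wording point. Both evaluable sizes are carried below.

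**2. If 14 and 2 are change SDs.** A Welch test of change has the power in step 1. A test of 16-week means also carries baseline spread. With correlation *r* between baseline and change in the exercise arm (zero in controls), the variances are b² + 14² + 2·r·b·14 and b² + 2². Example with b = 8, r = 0, 24 + 12: SE = √(260/24 + 68/12) = √16.5 = 4.06, 9/SE = 2.22, power 57.6%.

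| Power of 16-week means (%) | b = 4 | 6 | 8 | 10 | 12 |
|---|---|---|---|---|---|
| 24 + 12, r = 0 | 76.7 | 67.9 | 57.6 | 47.9 | 39.5 |
| 24 + 12, r = −0.5 | 86.3 | 81.0 | 71.7 | 60.5 | 49.8 |
| 22 + 11, r = 0 | 72.8 | 63.8 | 53.8 | 44.4 | 36.6 |
| 22 + 11, r = −0.5 | 83.0 | 77.3 | 67.7 | 56.5 | 46.2 |

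Simulation at 24 + 12 agrees within half a point (76.6 down to 39.1 at r = 0). The baseline-adjusted analysis was simulated with a common slope, arm-specific variance, REML and Satterthwaite df. It gave 84–85% at 24 + 12 and about 79–82% at 22 + 11, no material gain over a test of change. Type I error was 4.7–5.3% for the adjusted analysis and 4.7–5.4% for the unadjusted tests.

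**3. If 14 and 2 are week-16 level SDs.** The test of 16-week means now has the power in step 1. A test of change has variances b² + 14² − 2·r·b·14 and b² + 2² − 2·r·b·2, where *r* is the baseline-to-week-16 correlation in both arms. At 24 + 12:

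| Power (%) | r = 0 | 0.3 | 0.5 | 0.7 |
|---|---|---|---|---|
| Change, b = 4 | 76.7 | 83.9 | 88.8 | 93.3 |
| Change, b = 8 | 57.6 | 68.2 | 76.9 | 86.5 |
| Change, b = 12 | 39.5 | 47.3 | 54.4 | 63.5 |
| Adjusted (simulated) | 84 | 85 | 87 | 90 |

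The low cells pair a wide baseline spread with a control SD of 2 at week 16. If controls do not change, their baseline SD would also be near 2, and the change test then has about 82–91%.

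**4. Chance imbalance.** The SE of the baseline difference at 24 + 12 is b·√(1/24 + 1/12) = 0.354·b. The probability that it exceeds 4.5 ng/mL (half the target) in either direction is 11, 20 and 29% for b = 8, 10 and 12. Under the change reading, each 1 ng/mL of imbalance moves the 16-week estimate by 1 + 14r/(3b), which is 0.71 to 1.00 for b = 8–12 and r from −0.5 to 0. It moves the change estimate by 14r/(3b), which is −0.29 to 0. The adjusted estimate moved by −0.25 to 0 in simulation.

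**The case against.** The strongest reply is that 16-week means is loose wording for mean change. Section 8.2 speaks of change, of a percentage reduction and of no change in controls, and an SD of 2 on levels of 35–45 ng/mL looks more like a change SD. The Welch test also stands only in the sample-size section, so it is a planning test, not a committed analysis. On that reading a Welch test of change removes the loss in step 2, and adjustment adds nothing material. All of this stands. It is why a test of change is accepted below as a minimum, but 8.2 would still need rewording and 8.3 would still name no primary analysis.

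Four stronger readings are tempting, and the documents do not support them:

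- *Baseline PAI-1 is ignored.* A change endpoint cannot be computed without it. It is missing only as a named covariate.
- *The trial has 39–77% power.* That needs change SDs combined with a test of levels, and the baseline SDs are assumed.
- *The planned test is invalid.* Its type I error is about 5%.
- *Adjustment guarantees 84%.* That holds at 24 + 12, not at the 22 + 11 behind the stated power.

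The imbalance figures also do not favour adjustment over change, since both remove most of the effect.

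**Conclusion.** The point holds as a mismatch between the endpoint and the one test tied to it, with no primary analysis named to settle it. Matched readings show no shortfall. Under the change reading, testing 16-week means as 8.2 is worded would cost from nothing (small baseline SD with a negative correlation) to about 45 points at 24 + 12 (84.3 − 39.5). Under the level reading, a change-score test could lose as much, though only with a wide baseline spread that fits poorly with a control SD of 2.

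The baseline-adjusted analysis is the only one of the three that avoids large losses under both readings. These sizes rest on assumed baseline SDs and correlations. The textual finding does not. It should be corrected, but it does not threaten the trial's validity.

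**What to change.** - **8.3:** name one primary analysis: end-of-programme PAI-1 by randomised arm, adjusted for baseline PAI-1, with residual variance allowed to differ by arm, reporting the adjusted difference with its 95% CI. In SAS 9.4 this can be PROC MIXED with a REPEATED statement, GROUP= arm and Satterthwaite df. Unequal variance matters: with SDs of 14 and 2 at 24 + 12, a pooled Student's t has about 60% power against 84% for Welch.
- **8.2:** describe the target as the *difference in change in PAI-1*, and state whether 14 and 2 are level or change SDs.
- **Acceptable minimum:** if they are confirmed as change SDs, a Welch test of change named in 8.3.

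The cost is one sentence in 8.3 and a wording correction in 8.2, with no new data or visits. Adjustment can lose about 1 to 4 points of power in some cells with a small baseline SD and strong correlation. At baseline SD 4 and r = −0.7 under the change reading, it has 85.6% against 90.0% for 16-week means. At baseline SD 4 and r = 0.7 under the level reading, it has 89.8% against 93.3% for change.
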